861611000000100'		Education about anxiety (procedure)
89948007'		Panic disorder with agoraphobia AND mild panic attacks (disorder)
90790003'		Avoidant disorder of adolescence (disorder)
94641000119109'		Anxiety in pregnancy (disorder)

Eating disorders

Read V2 Code	Term ID	Description
Read CTV3 Code	Term ID	Description
SNOMED Code	Term ID	Description

Body image disorders		
Read V2 Code	Term ID	Description
Read CTV3 Code	Term ID	Description
SNOMED Code	Term ID	Description
Attention-deficit disorder (ADHD)		
Read V2 Code	Term ID	Description
Read CTV3 Code	Term ID	Description
SNOMED Code	Term ID	Description
Behavioural disorders		
Read V2 Code	Term ID	Description
Read CTV3 Code	Term ID	Description
SNOMED Code	Term ID	Description
Adjustment disorder		
Read V2 Code	Term ID	Description
E29..	All	Adjustment reaction
E290.	All	Brief depressive reaction
E2900	All	Grief reaction
E290z	All	Brief depressive reaction NOS
E291.	All	Prolonged depressive reaction
E292.	All	Adjustment reaction with predominant disturbance of other emotions
E2924	All	Adjustment reaction with anxious mood
E292y	All	Adjustment reaction with mixed disturbance of emotion
E292z	All	Adjustment reaction with disturbance of other emotion NOS
E293.	All	Adjustment reaction with predominant disturbance of conduct
E2930	All	Adjustment reaction with aggression
E2931	All	Adjustment reaction with antisocial behaviour

E2932	All	Adjustment reaction with destructiveness
E293z	All	Adjustment reaction with predominant disturbance of conduct NOS
E294.	All	Adjustment reaction with mixed disturbance of emotion and conduct
E29y.	All	Other adjustment reactions
E29y2	All	Adjustment reaction with physical symptoms
E29y3	All	Elective mutism due to an adjustment reaction
E29y5	All	Other adjustment reaction with withdrawal
E29yz	All	Other adjustment reactions NOS
E29z.	All	Adjustment reaction NOS
Read CTV3 Code	Term ID	Description
E29..	All	Adjustment disorder
E290.	All	Brief depressive adjustment reaction
E290z	All	Brief depressive reaction NOS
E291.	All	Prolonged depressive adjustment reaction
E2924	All	Adjustment reaction with anxious mood
E292y	All	Adjustment reaction with mixed disturbance of emotion
E293.	All	Adjustment reaction with predominant disturbance of conduct
E2930	All	Adjustment reaction with aggression
E2931	All	Adjustment reaction with antisocial behaviour
E2932	All	Adjustment reaction with destructiveness
E293z	All	Adjustment reaction with predominant disturbance of conduct NOS
E294.	All	Adjustment reaction with mixed disturbance of emotion and conduct
E292.	All	Adjustment reaction with predominant disturbance of other emotions
E292z	All	Adjustment reaction with disturbance of other emotion NOS
E29y.	All	Other adjustment reactions
E29yz	All	Other adjustment reactions NOS

E29y2	All	Adjustment reaction with physical symptoms
E29y3	All	Elective mutism due to an adjustment reaction
E29y5	All	Other adjustment reaction with withdrawal
E29z.	All	Adjustment reaction NOS
SNOMED Code	Term ID	Description
17226007		Adjustment disorder (disorder)
15977008		Adjustment disorder with academic inhibition (disorder)
47372000		Adjustment disorder with anxious mood (disorder)
57194009		Adjustment disorder with depressed mood (disorder)
192046006		Brief depressive adjustment reaction (disorder)
192049004		Prolonged depressive adjustment reaction (disorder)
84984002		Adjustment disorder with disturbance of conduct (disorder)
66381006		Adjustment disorder with mixed disturbance of emotions AND conduct (disorder)
192056005		Adjustment reaction with aggression (disorder)
192057001		Adjustment reaction with antisocial behavior (disorder)
192058006		Adjustment reaction with destructiveness (disorder)
55668003		Adjustment disorder with mixed emotional features (disorder)
18478005		Adjustment disorder with physical complaints (disorder)
9674006		Adjustment disorder with withdrawal (disorder)
32880007		Adjustment disorder with work inhibition (disorder)
386821008		Adjustment reaction in infancy (disorder)
386822001		Adjustment reaction of adolescence (disorder)
386823006		Adjustment reaction of adult life (disorder)
386824000		Adjustment reaction of childhood (disorder)

386825004		Adjustment reaction of late life (disorder)
425914008		Adjustment reaction to medical therapy (disorder)
192063005		Adjustment reaction with physical symptoms (disorder)
192064004		Elective mutism due to an adjustment reaction (disorder)
698697003		Adjustment disorder with mixed disturbance of emotions and conduct in remission (disorder)
Acute stress disorder		
Read V2 Code	Term ID	Description
Read CTV3 Code	Term ID	Description
SNOMED Code	Term ID	Description
Schizophrenia		
Read V2 Code	Term ID	Description
Read CTV3 Code	Term ID	Description
SNOMED Code	Term ID	Description
Post-traumatic stress disorder		
Read V2 Code	Term ID	Description
Read CTV3 Code	Term ID	Description
SNOMED Code	Term ID	Description
Bipolar disorder		
Read V2 Code	Term ID	Description
Read CTV3 Code	Term ID	Description
SNOMED Code	Term ID	Description

sTable 2.2 Algorithms used to identify anxiety episodes, depression episodes, and recurrent major depression. Expressions in capitals equate to Boolean expressions. *More than 1 year ago. SSRIs = selective serotonin reuptake inhibitors, TCA = tricyclic antidepressants, MAOI = monoamine oxidase inhibitors, CBT = cognitive behavioural therapy.

Clinical entity	Definition
Anxiety	Any coded anxiety episode AND concurrent treatment for anxiety
Depressive episode	Any coded depressive episode AND concurrent treatment for depression
Recurrent depressive disorder	(Any historical code* for a depressive episode AND current treatment for depression) OR Any code for recurrent depressive disorder
Anxiety treatments	SSRIs, anxiolytics, counselling, CBT, and psychotherapy
Depression treatments	SSRIs, TCAs, MAOIs, counselling, CBT, and psychotherapy

sTable 2.3 WHO International Statistical Classification of Diseases (ICD-10) for mental health conditions

Clinical entity	ICD 10 code	Definition
Depressive episode	F32	Any coded depressive episode AND concurrent treatment for depression
Recurrent depressive disorder	F33	(Any historical code* for a depressive episode AND current treatment for depression) OR Any code for recurrent depressive disorder
Depression treatments	NA	SSRIs, TCAs, MAOIs, counselling, CBT, and psychotherapy
Anxiety	F41	Any coded anxiety episode AND concurrent treatment for anxiety
Anxiety treatments	NA	SSRIs, anxiolytics, counselling, CBT, and psychotherapy
Self-harm	X60-X84	Any diagnostic or indicative code for any form of self-harm, including suicide attempt
Eating disorders	F50	Any diagnostic or indicative code for eating disorders

Body image disorders	F45.2	Any diagnostic or indicative code for body image / dysmorphic disorder (excluding hypochondriacal disorders not associated with body image)
Attention-deficit disorders	F90.0	Any diagnostic or indicative code for disturbance of activity and attention
Behavioural disorders	F91 F92	Any diagnostic or indicative code for conduct disorders
Adjustment disorders	F43.2	Any diagnostic or indicative code for adjustment disorders
Acute stress disorders	F43.0	Any diagnostic or indicative code for acute stress disorders
Post-traumatic stress disorder	F43.1	Any diagnostic or indicative code for Post-traumatic stress disorder

Appendix 3

sTable 3.1 Read and SNOMED codes to be used to identify quality of life

Depressive episode		
Read V2 Code	Term ID	Description
E112.	All	Single major depressive episode
E1120	All	Single major depressive episode, unspecified
E1121	All	Single major depressive episode, mild
E1122	All	Single major depressive episode, moderate
E1123	All	Single major depressive episode, severe, without mention of psychosis
E1124	All	Single major depressive episode, severe, with psychosis
E1125	All	Single major depressive episode, in partial or unspecified remission
E1126	All	Single major depressive episode, in full remission
E112z	All	Single major depressive episode NOS
E113.	All	Recurrent major depressive episode
E1130	All	Recurrent major depressive episodes, unspecified
E1131	All	Recurrent major depressive episodes, mild
E1132	All	Recurrent major depressive episodes, moderate
E1133	All	Recurrent major depressive episodes, severe, without mention of psychosis
E1134	All	Recurrent major depressive episodes, severe, with psychosis
E1137	All	Recurrent depression
E113z	All	Recurrent major depressive episode NOS
E118.	All	Seasonal affective disorder
E11y2	All	Atypical depressive disorder
E11z2	All	Masked depression
E130.	All	Reactive depressive psychosis

E135.	All	Agitated depression
E2003	All	Anxiety with depression
E291.	All	Prolonged depressive reaction
E2B..	All	Depressive disorder NEC
E2B1.	All	Chronic depression
E2B0.	All	Postviral depression
Eu204	All	[X]Post-schizophrenic depression
Eu251	All	[X]Schizoaffective disorder, depressive type
Eu32.	All	[X]Depressive episode
Eu320	All	[X]Mild depressive episode
Eu321	All	[X]Moderate depressive episode
Eu322	All	[X]Severe depressive episode without psychotic symptoms
Eu323	All	[X]Severe depressive episode with psychotic symptoms
Eu324	All	[X]Mild depression
Eu325	All	[X]Major depression, mild
Eu326	All	[X]Major depression, moderately severe
Eu327	All	[X]Major depression, severe without psychotic symptoms
Eu328	All	[X]Major depression, severe with psychotic symptoms
Eu32y	All	[X]Other depressive episodes
Eu32z	All	[X]Depressive episode, unspecified
Eu33.	All	[X]Recurrent depressive disorder
Eu330	All	[X]Recurrent depressive disorder, current episode mild
Eu331	All	[X]Recurrent depressive disorder, current episode moderate
Eu332	All	[X]Recurrent depressive disorder, current episode severe without psychotic symptoms
Eu333	All	[X]Recurrent depressive disorder, current episode severe with psychotic symptoms

Eu334	All	[X]Recurrent depressive disorder, currently in remission
Eu33y	All	[X]Other recurrent depressive disorders
Eu33z	All	[X]Recurrent depressive disorder, unspecified
Eu412	All	[X]Mixed anxiety and depressive disorder
Read CTV3 Code	Term ID	Description
X00Sb	All	Mixed anxiety and depressive disorder
X00SO	All	Depressive disorder
X761L	All	Seasonal affective disorder
Xa0wV	All	Recurrent brief depressive disorder
X00SQ	All	Agitated depression
XE1YC	All	Reactive depression
X00SR	All	Endogenous depression
X00SS	All	Endogenous depression first episode
XE1Y0	All	Single major depressive episode
E1120	All	Single major depressive episode, unspecified
E1121	All	Single major depressive episode, mild
E1122	All	Single major depressive episode, moderate
E1123	All	Single major depressive episode, severe, without mention of psychosis
E1124	All	Single major depressive episode, severe, with psychosis
XaX53	All	Single major depressive episode, severe, with psychosis, psychosis in remission
E1125	All	Single major depressive episode, in partial or unspecified remission
E1126	All	Single major depressive episode, in full remission
E112z	All	Single major depressive episode NOS
XM1GC	All	Endogenous depression - recurrent
E1130	All	Recurrent major depressive episodes, unspecified
E1131	All	Recurrent major depressive episodes, mild

E1132	All	Recurrent major depressive episodes, moderate
E1133	All	Recurrent major depressive episodes, severe, without mention of psychosis
E1134	All	Recurrent major depressive episodes, severe, with psychosis
E1135	All	Recurrent major depressive episodes, in partial or unspecified remission
E1136	All	Recurrent major depressive episodes, in full remission
E113z	All	Recurrent major depressive episode NOS
X00SU	All	Masked depression
E11y2	All	Atypical depressive disorder
X00S8	All	Post-schizophrenic depression
XSEGJ	All	Major depressive disorder
XSKr7	All	Cotard syndrome
XSGol	All	Moderate major depression
XSGok	All	Mild major depression
XGom	All	Severe major depression without psychotic features
XGon	All	Severe major depression with psychotic features
E1137	All	Recurrent depression
E130.	All	Reactive depressive psychosis
E2B..	All	Depressive disorder NEC
E2B0.	All	Postviral depression
E2B1.	All	Chronic depression
Eu320	All	[X]Mild depressive episode
Eu321	All	[X]Moderate depressive episode
Eu331	All	[X]Recurrent depressive disorder, current episode moderate
XE1Y1	All	Recurrent major depressive episodes
XE1ZY	All	[X]Severe depressive episode without psychotic symptoms
XE1ZZ	All	[X]Severe depressive episode with psychotic symptoms

XE1Za	All	[X]Other depressive episodes
XE1Zb	All	[X]Depressive episode, unspecified
XE1Zd	All	[X]Recurrent depressive disorder, current episode severe without psychotic symptoms
XE1Ze	All	[X]Recurrent depressive disorder, current episode severe with psychotic symptoms
XE1Zf	All	[X]Recurrent depressive disorder, unspecified
XaB9J	All	Depression NOS
XaCHr	All	[X] Single episode agitated depression without psychotic symptoms
XaCHs	All	[X] Single episode major depression without psychotic symptoms
XaCIs	All	Mild depression
XaCIt	All	Moderate depression
XaClu	All	Severe depression
SNOMED Code	Term ID	Description
832007'		Moderate major depression (disorder)
2618002'		Chronic recurrent major depressive disorder (disorder)
14070001'		Multi-infarct dementia with depression (disorder)
14183003'		Chronic major depressive disorder, single episode (disorder)
15193003'		Severe recurrent major depression with psychotic features, mood-incongruent (disorder)
15639000'		Moderate major depression, single episode (disorder)
18818009'		Moderate recurrent major depression (disorder)
19527009'		Single episode of major depression in full remission (disorder)
20250007'		Severe major depression, single episode, with psychotic features, mood-incongruent (disorder)
25922000'		Major depressive disorder, single episode with postpartum onset (disorder)
28475009'		Severe recurrent major depression with psychotic features (disorder)

30605009'		Major depression in partial remission (disorder)
33078009'		Severe recurrent major depression with psychotic features, mood-congruent (disorder)
33135002'		Recurrent major depression in partial remission (disorder)
33736005'		Severe major depression with psychotic features, mood-congruent (disorder)
35489007'		Depressive disorder (disorder)
36474008'		Severe recurrent major depression without psychotic features (disorder)
36923009'		Major depression, single episode (disorder)
38694004'		Recurrent major depressive disorder with atypical features (disorder)
39809009'		Recurrent major depressive disorder with catatonic features (disorder)
40379007'		Mild recurrent major depression (disorder)
40568001'		Recurrent brief depressive disorder (disorder)
42925002'		Major depressive disorder, single episode with atypical features (disorder)
48589009'		Minor depressive disorder (disorder)
58703003'		Postpartum depression (disorder)
60099002'		Severe major depression with psychotic features, mood-incongruent (disorder)
66344007'		Recurrent major depression (disorder)
69392006'		Major depressive disorder, single episode with catatonic features (disorder)
70747007'		Major depression single episode, in partial remission (disorder)
71336009'		Recurrent major depressive disorder with postpartum onset (disorder)
73867007'		Severe major depression with psychotic features (disorder)
75084000'		Severe major depression without psychotic features (disorder)
76441001'		Severe major depression, single episode, without psychotic features (disorder)
77911002'		Severe major depression, single episode, with psychotic features, mood-congruent (disorder)
79298009'		Mild major depression, single episode (disorder)
79842004'		Stuporous depression (disorder)

82218004'		Postoperative depression (disorder)
83458005'		Agitated depression (disorder)
87414006'		Reactive depression (situational) (disorder)
87512008'		Mild major depression (disorder)
161469008'		History of depression (situation)
191495003'		Drug-induced depressive state (disorder)
191604000'		Single major depressive episode, severe, with psychosis (disorder)
191610000'		Recurrent major depressive episodes, mild (disorder)
191611001'		Recurrent major depressive episodes, moderate (disorder)
191613003'		Recurrent major depressive episodes, severe, with psychosis (disorder)
191616006'		Recurrent depression (disorder)
191659001'		Atypical depressive disorder (disorder)
191676002'		Reactive depressive psychosis (disorder)
192046006'		Brief depressive adjustment reaction (disorder)
192049004'		Prolonged depressive adjustment reaction (disorder)
192079006'		Postviral depression (disorder)
192080009'		Chronic depression (disorder)
231485007'		Post-schizophrenic depression (disorder)
231499006'		Endogenous depression first episode (disorder)
231500002'		Masked depression (disorder)
231504006'		Mixed anxiety and depressive disorder (disorder)
237349002'		Mild postnatal depression (disorder)
237350002'		Severe postnatal depression (disorder)
237739002'		Pseudo-Cushing's syndrome of depression (disorder)
247803002'		Seasonal affective disorder (disorder)
268621008'		Recurrent major depressive episodes (disorder)

272022009'		Complaining of feeling depressed (finding)
274948002'		Endogenous depression - recurrent (disorder)
300706003'		Endogenous depression (disorder)
310495003'		Mild depression (disorder)
310496002'		Moderate depression (disorder)
310497006'		Severe depression (disorder)
319768000'		Recurrent major depressive disorder with melancholic features (disorder)
320751009'		Major depression, melancholic type (disorder)
321717001'		Involutional depression (disorder)
366979004'		Depressed mood (finding)
370143000'		Major depressive disorder (disorder)
394924000'		Symptoms of depression (finding)
395072006'		Counseling for postnatal depression (procedure)
430852001'		Severe major depression, single episode, with psychotic features (disorder)
450714000'		Severe major depression (disorder)
704678007'		Depressed mood with postpartum onset (finding)
712823008'		Acute depression (disorder)
718636001'		Minimal depression (disorder)
719592004'		Moderately severe major depression (disorder)
719593009'		Moderately severe depression (disorder)
720451004'		Minimal recurrent major depression (disorder)
720452006'		Moderately severe recurrent major depression (disorder)
720453001'		Moderately severe major depression single episode (disorder)
720454007'		Minimal major depression single episode (disorder)
720455008'		Minimal major depression (disorder)
723928009'		Mood disorder with depressive symptoms caused by alcohol (disorder)

723930006'		Mood disorder with mixed manic and depressive symptoms caused by alcohol (disorder)
724676000'		Mood disorder with depressive symptoms caused by sedative (disorder)
724677009'		Mood disorder with depressive symptoms caused by hypnotic (disorder)
724678004'		Mood disorder with depressive symptoms caused by anxiolytic (disorder)
724690002'		Mood disorder with depressive symptoms caused by cocaine (disorder)
724757005'		Depressive symptoms due to primary psychotic disorder (disorder)
726772006'		Major depression with psychotic features (disorder)
762321000'		Mood disorder with depressive symptoms caused by opioid (disorder)
762329003'		Mood disorder with depressive symptoms caused by stimulant (disorder)
762336002'		Mood disorder with depressive symptoms caused by hallucinogen (disorder)
762339009'		Mood disorder with depressive symptoms caused by volatile inhalant (disorder)
		Mood disorder with depressive symptoms caused by synthetic cathinone (disorder)
762512002'		Depression care management (procedure)
768835002'		Antenatal depression (disorder)
838529004'		Mood disorder with mixed depressive and manic symptoms caused by amphetamine and amphetamine derivative (disorder)
871840004'		Episode of depression (finding)
251000119105'		Severe major depression, single episode (disorder)

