The eligible PIBD cases will comprise all incident cases of PIBD over the last decade, we will not follow patients up beyond 01/01/2020 due to changes in patient health behaviour and primary care interactions due to COVID-19. We will extract sociodemographic details for all these cases and matched controls (described below). Sociodemographic data will comprise by age group, gender, ethnicity, and socioeconomic status. Ethnicity will be categorised as follows to be consistent with the UK official census categories: White, Asian, Black African/Caribbean, Mixed, and Other. The index of multiple deprivation (IMD) will be used as a measure of socioeconomic status. This is derived from patient postcode at the point of data extraction.

Stream 1: Definition of matched controls without IBD

We will match each incident case of PIBD with controls (children without IBD) using propensity score matching (matching on the sociodemographic variables list above and matching within primary care practice if numbers allow). People with a known diagnosis of irritable bowel syndrome (IBS) will be excluded from the potential pool of controls. We will compare the incidence of new onset mental health conditions in PIBD and controls using a similar approach to that used by Butwick et al. (2019) in their paper exploring psychiatric disorders in a

PIBD cohort in Sweden.(9) The mental health conditions to be examined are listed in table 1 although there is scope to add to or modify these in discussion with the study authors. For a composite 'any psychological condition' outcome (see Table 1), risk will be stratified by age of PIBD onset and sex.

We will then go beyond the analysis of the Swedish study to estimate the cumulative risk of the 'any psychological condition' composite outcome in PIBD patients compared with controls. This will provide a unique, robust, estimate of the overall mental health burden (prevalence) in PIBD.

Condition	Description
Primary outcomes	
Any psychological condition	A composite of all the chronic psychiatric conditions listed below* (depression, anxiety, eating disorders, body image disorder, attention-deficit disorder, behavioural disorders, adjustment disorder, acute stress disorder, and post-traumatic stress disorder)
Depression	Major recurrent depression or treated depressive episode
Anxiety	Non-phobia related anxiety episodes or disorder
Secondary outcomes	
Self-harm	Any coded episode of deliberate self-harm of any type

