Cox proportional hazards models will be used to compare disease incidence in PIBD cases and controls and also when comparing the associations of baseline features and outcomes within the PIBD cohort. The study start date will be the date of diagnosis of PIBD or, for controls, the date of diagnosis of their matched counterpart. The end of follow-up will be the first of; the point of data extraction (**exact date TBC**), the patient's 25th birthday, date of loss to follow-up (either GP practice deregistration or death). All individuals contributing at least six months of follow-up time in the analysis will be included. Those with existing evidence of the mental health condition prior to baseline will be excluded for analysis of that particular outcome where it would not reoccur, for example if individual has already received a diagnosis of recurrent depressive disorder they would not receive this diagnosis again, although conditions at baseline that can reoccur, such as suicide attempt, would not be excluded. Models will be adjusted for age, gender, socioeconomic status, ethnicity, and other childhood conditions (asthma, atopic dermatitis, allergic rhinitis, thyroid disease, epilepsy, diabetes, cancer, juvenile idiopathic arthritis (JIA) including systemic JIA, systemic lupus erythematosus (lupus), ankylosing spondylitis (AS) and psoriatic arthritis). Statistical significance for analyses will be reported using P values and 95% confidence intervals as appropriate.

Cumulative risk (i.e. prevalence) of the 'any psychological condition' composite outcome will be evaluated up to age 25. Cumulative incidence will be calculated by using methods to estimate risk similar to those recently published when assessing lifetime risk of other chronic conditions in the Lancet.(11, 12) Key outputs will be cumulative risk plots, presenting the cumulative incidence of the outcome by age for PIBD patients compared to controls. At a particular age, the cumulative incidence estimate can be interpreted as the lifetime incidence of the outcome up until the year of age in question. Childhood cumulative risk will be defined as the cumulative incidence at age 18.

Stream 1: Sensitivity analysis

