At the index date, we will define groups in the IBD case population based on mental health phenotype, including a comparator group without mental health comorbidity at the index date, and compare the sociodemographic characteristics of these groups.

Stream 2: Follow-up

We will then describe incidence of each study outcome in the five years after the index date for each group, and the relative incidence of each outcome in those with and without mental health comorbidity.

Stream 2: Study outcomes

These will comprise the following.

Quality of life indicators:

Affective symptoms (depression, low mood, deliberate self-harm, suicidal ideation or parasuicide), IBD symptoms, absence from school, absence from work, unemployment, substance abuse, and sleep problems. IBD symptoms will comprise; abdominal pain, discomforts or bloating, diarrhoea, weight loss, growth retardation and tiredness/fatigue. (See Appendix 1 – Table s1 for Read Codes and SNOMED codes).

IBD severity indicators:

Medication use, surgical intervention, nutritional supplement use, and markers of nutritional status. Surgical intervention will comprise any abdominal surgery, and stoma formation (as a separate outcome). Medication use will comprise use of: rectal 5-aminosalicylic acid (5-ASA), oral 5-ASA, rectal steroids, oral steroids, antimetabolites, tumour necrosis factor inhibitors (TNFi) and other biologic therapies. The latter of these groups may not be well captured in primary care and if so this will be reported in the limitations section of the final study manuscript. Nutritional supplements will comprise the five most prescribed nutritional supplements: Modulen, Fortisip, Ensure, Osmolite, and Neocate. Nutritional markers will comprise; being underweight (under the 5th centile of weight for height or BMI < 18.5 kg/m² after age 18) and growth retardation related codes. (See Appendix 1 – Table s2 for Read Codes and SNOMED codes).

Healthcare resource utilisation:

Primary care attendances and hospital admissions. Hospital admissions will be separated into general admissions (including those for IBD) and psychiatric admissions. (See Appendix 1 – Table s2 for Read Codes and SNOMED codes).

Stream 2: Statistical methods

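### A tricyclic prescribed for any reason can confirm a depression outcome, and the plan has no check on whether this differs between IBD cases and controls

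*Combined protocol and SAP*

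**What the plan says.** Depression is a primary outcome of Stream 1. Table 1 describes it as "Major recurrent depression or treated depressive episode", and it is also part of the composite of any psychological condition. Appendix 2, sTable 2.2 makes this operational in two ways.

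- For a single episode, the rule reads "Any coded depressive episode AND concurrent treatment for depression".
- For the recurrent form, the rule has two alternatives and reads ("Any historical code* for a depressive episode AND current treatment for depression) OR Any code for recurrent depressive disorder". The asterisk means more than one year ago.

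The depression treatments are "SSRIs, TCAs, MAOIs, counselling, CBT, and psychotherapy". The table's note adds that "Expressions in capitals equate to Boolean expressions". The lower-case conjunction in the treatment list is therefore an ordinary list, and any single item is enough. No indication, dose, duration or time window is given. sTable 2.3 repeats the same rules. The anxiety treatment list contains no TCAs, so the point concerns depression only.

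On the comparison, the section on the incidence of mental health conditions states: "Cox proportional hazards models will be used to compare disease incidence in PIBD cases and controls". The section on matched controls states: "People with a known diagnosis of irritable bowel syndrome (IBS) will be excluded from the potential pool of controls". For Stream 2, the outcomes section states: "IBD symptoms will comprise; abdominal pain, discomforts or bloating, diarrhoea, weight loss, growth retardation and tiredness/fatigue".

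**The concern.** The treatment requirement does much of the work of making the depression outcome specific. The code list in sTable 2.1 is broad: besides diagnoses, it includes SNOMED codes for a history of depression, depressed mood, symptoms of depression and a complaint of feeling depressed. If a drug given for another reason can satisfy the treatment requirement, part of that specificity is lost.

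This matters for the comparison only if the loss is uneven. TCAs can be prescribed for non-psychiatric reasons such as pain. That is general knowledge, which the documents do not state, and it is treated here as an assumption. If it holds, two features of the plan make unevenness plausible: abdominal pain belongs to the exposure, and one group with abdominal symptoms is missing from the comparator. Outcome misclassification would then depend on exposure, for a primary outcome of Stream 1.

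Stream 2 raises a related issue that needs no case-control difference. If patients with a depression code enter the depression phenotype on the strength of a TCA taken for pain, a later comparison of abdominal pain between phenotypes is partly built in. Abdominal pain is one of the quality-of-life indicators under that stream's primary objective.

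**Working it through.** **No figure to reproduce.** The documents give no TCA prescribing rate, no share of coded depression that is treated and no event count. All inputs below are assumptions. They show how the size behaves and do not estimate it.

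**Episode limb.** Let u be the share of coded depression with no other listed treatment. Let p1 and p0 be the shares of these with a TCA for pain, in cases and controls. With a true ratio of 1.00,

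apparent ratio = [(1 − u) + u·p1] / [(1 − u) + u·p0].

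| u | p1 | p0 | calculation | ratio |
|---|---|---|---|---|
| 30% | 5% | 2% | 0.715 / 0.706 | 1.013 |
| 30% | 5% | 1% | 0.715 / 0.703 | 1.017 |
| 30% | 10% | 2% | 0.730 / 0.706 | 1.034 |
| 30% | 10% | 1% | 0.730 / 0.703 | 1.038 |
| 60% | 5% | 2% | 0.430 / 0.412 | 1.044 |
| 60% | 5% | 1% | 0.430 / 0.406 | 1.059 |
| 60% | 10% | 2% | 0.460 / 0.412 | 1.117 |
| 60% | 10% | 1% | 0.460 / 0.406 | 1.133 |

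Six of the eight values lie between 1.01 and 1.06. The two larger ones need u = 60% together with a five- to tenfold prescribing difference. If p1 = p0, numerator and denominator are equal and the ratio is 1.00 for every u.

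**Historical-code limb.** Let t be the share of people with an old depression code who are currently treated for depression. Then

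apparent ratio = [t + (1 − t)·p1] / [t + (1 − t)·p0].

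With p1 = 5% and p0 = 1%:

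- t = 50%: 0.525 / 0.505 = 1.040
- t = 20%: 0.240 / 0.208 = 1.154
- t = 10%: 0.145 / 0.109 = 1.330

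This limb is the more exposed, because nothing links the old code and the current drug in time. It contributes only part of the depression events, so these ratios do not carry over to the whole outcome.

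**What both formulas leave out.** They ignore TCAs truly given for depression, and patients who qualify by a recurrent-depression code with no treatment at all. Both omissions make the ratios too far from 1.

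**Does the plan handle it elsewhere?** The adjustment sets in both streams list demographics and comorbid conditions. They include neither abdominal pain nor the reason for a prescription. The one stated Stream 1 sensitivity analysis restricts controls to recent attenders, which does not test the treatment requirement. Stream 2 states none.

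**The case against.** The strongest reply is that the causal premise lies outside the documents. They do not say that TCAs are given for pain, or that they are given more often in IBD than in controls. That stands, and it limits the point to a possibility. A reader might infer that the depression hazard ratio is inflated, but the documents do not support this.

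Four further limits stand.

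- A reader might infer that the same record counts as an event in a case and not in a control. It does not: one algorithm applies to both groups, and only the frequency of such records could differ.
- A TCA cannot create an event by itself. A depression code is always required, and the table speaks of treatment for depression, although it gives no rule for establishing that intent.
- The composite has nine components, so any effect on it is diluted.
- The net direction is open. The Stream 1 methods exclude people with prior evidence of a condition that would not recur. If the historical-code rule is applied before baseline, TCA use could remove more IBD patients from the risk set, which may act the other way. The example given there is an existing recurrent diagnosis, so it is unclear whether someone with a single old episode stays at risk.

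For Stream 2, a reader might infer that circularity is certain. The cohort section names a phenotype of major depression or depressive episodes, omits Table 1's word for treated, and says only that an algorithm will be developed. The reference to the algorithm tables sits under the Stream 1 outcome table. That sTable 2.2 applies to Stream 2 is therefore an inference.

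**Conclusion.** The point holds as a gap that the plan leaves untested. As written, one TCA prescription for any indication can meet the treatment requirement in both depression limbs, and no planned analysis shows how often it does or whether this differs by IBD status.

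Under the assumed inputs for the episode limb, a true hazard ratio of 1.00 becomes about 1.01 to 1.13, mostly near the lower end. The historical-code limb can move more but contributes only part of the events. These figures require higher TCA use for pain in cases than in controls, which is plausible but undocumented. The Stream 2 concern is conditional on the same algorithm defining the phenotype. This is a cheap improvement and does not invalidate the primary analysis.

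**What to change.** Keep the primary algorithm unchanged and add the following.

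1. Report the number of TCA-only confirmations (a TCA as the only listed treatment and no recurrent-depression code) by group and by limb (episode, historical code). This requires stating the window that counts as concurrent.
2. Prespecify a sensitivity analysis that treats TCA-only patients as not meeting the algorithm. Apply it identically to cases and controls, both at baseline exclusion and at outcome.
3. Run it for the Stream 1 depression and composite hazard ratios and for the Stream 2 abdominal-pain comparison. State whether sTable 2.2 defines the Stream 2 depression phenotype.

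A stricter primary rule, such as counting a TCA only when first issued at the coding consultation, is not recommended. It would drop TCAs started at a follow-up visit and those already in use when depression is newly coded, and that loss could itself differ by group.

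The cost is one extra run on prescription records the study already uses. Some true TCA-treated depressions are lost, in that run only.
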